## 7.6. 90 Day (±14 Days) Follow-up

- NIHSS (optional - to be collected only if performed per SOC)
- An mRS assessment must be conducted. This mRS assessment must be performed by a qualified evaluator who is independent of the interventional treating team and the subject's direct clinical care (e.g., neurologist, CRNC).
- Record any reportable AEs per this protocol which occurred after 7 day / discharge time point and up to the time of the 90-day examination.

Any study subject who does not attend a scheduled follow-up visit should be contacted by site personnel to determine the reason for the missed appointment and rescheduled. The 90-day assessments may be done via telephone (reportable AEs, mRS).

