7.3	Demographic and Baseline Characteristics.....	7
7.4	Procedural Characteristics.....	7
7.5	Primary and Secondary Endpoints.....	7
7.5.1	Primary Endpoint.....	8
7.5.2	Secondary Endpoints	8
7.5.2.1	Secondary Effectiveness Endpoints.....	8
7.5.2.2	Secondary Safety Endpoints.....	9
7.6	Health Economic Endpoints.....	10
7.7	Clot Analysis	10
7.8	Analyses of Adverse Events (AEs).....	11
7.9	Plans for Interim Analyses	12
7.10	Handling of Missing Data	12
7.11	Sensitivity Analyses.....	12
7.12	Subgroup Analysis.....	12
7.13	Additional Analyses.....	13
7.14	Changes from Planned Analyses	13

1 Study Design

This is a prospective, multi-center, single-arm, post-market clinical follow-up study that will enroll approximately 100 subjects at approximately 10 sites primarily in Europe, with clot collection for follow-on histopathological analysis. Subjects will be included in the study for a period of 3 months after the procedure, including follow up visits at 24 hours, 7 days (or discharge) and 90 days after the procedure.

2 Treatment Assignment

This is a single arm study and all enrolled subjects are intended to be treated with the study device, the EMBOVAC Aspiration Catheter.

3 Interval Windows

Study reports will be summarized using analysis visits as defined below.

- 24 Hours post-procedure (-12 to +48 hours)
- 7-Day/Discharge (-1 to +7 days)
- 90-day follow-up (± 15 days)

The study schedule is to be adhered to as closely as possible for all subjects. Data will be summarized by scheduled visit. Measurements outside the analysis windows will be considered as missing in the analysis. In the case of repeated measurements taken at the same visit, the most recent measurement with non-missing values will be used unless specified otherwise.

4 Levels of Significance

No hypothesis tests are planned in the study. All confidence intervals will be reported at a two-sided 95% confidence level. These confidence intervals will not be used for statistical inferences, but for clinical reference purpose and are intended to convey precision in the estimates.

5 Analysis Sets

The following analysis sets are defined in the study:

- **Modified Intent-to-Treat (mITT) Analysis Set**

The mITT analysis set will consist of enrolled subjects who have received treatment (at least one pass; a pass being defined as use of aspiration followed by evaluation of revascularization with angiography) with the study device.

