- **Modified Rankin Scale (mRS) 0-2 at 90 days**

The number and percentage of subjects achieving mRS 0-2 at 90 days (75 days or above) will be summarized with CIs. Subjects with missing mRS scores due to all-cause mortality are considered to have an mRS score of 6 in the analysis, subjects with missing mRS scores due to reasons other than all-cause mortality will be excluded. Subjects with mRS scores outside or didn't reach the 90-day window, due to reasons other than mortality, will be listed together with their mTICI scores at end of procedure.

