7.14 Changes from Planned Analyses

- Analysis window mRS \leq 2 at 90-day

Due to the potential impact of Covid-19, it is expected that there may be more late 90-day mRS assessments compared to the SAP-defined 90-day window of ± 15 than

anticipated. In order to minimize the impact of out of 90-day window assessments, analyses on mRS endpoint will include all available assessments on or after 75 days. Analyses using the 90-day window of ± 15 days will be considered part of the sensitivity analyses (section 7.11).

Other study endpoints at 90 days (e.g., all-cause mortality at 90 days, device and/or procedure related SAEs at 90 days) will still be based on the 90-day window of ± 15 days considering the event days are not restricted by the compliance of the 90-day visit.

End of Document

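### The main analysis of mRS 0-2 at 90 days can count a subject who has died by day 90 as a success, and it reports scores of any lateness without the protocol-window rate beside them

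*SAP*

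**What the plan says.** Protocol 7.6 and Table 1 place the 90-day mRS at ±14 days and require an independent rater: "This mRS assessment must be performed by a qualified evaluator who is independent of the interventional treating team". Protocol 14 lists an out-of-window visit among its examples of protocol deviations.

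SAP 3 sets a 90-day analysis window of ±15 days and adds: "Measurements outside the analysis windows will be considered as missing in the analysis". For mRS, SAP 7.5.2.1 replaces this with an open-ended rule: "The number and percentage of subjects achieving mRS 0-2 at 90 days (75 days or above) will be summarized with CIs". SAP 7.14 confirms that "analyses on mRS endpoint will include all available assessments on or after 75 days" and gives the reason: "Due to the potential impact of Covid-19, it is expected that there may be more late 90-day mRS assessments". The ±15-day analysis on observed data becomes a sensitivity analysis (SAP 7.11). SAP 7.5.2.1 also lists subjects whose scores fall outside the 90-day window, with their end-of-procedure mTICI.

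On death, SAP 7.5.2.1 and Protocol 10.5.4.2.1 assign mRS 6 only where the score is missing because the subject died. Neither says what happens when a subject is rated inside the window and then dies by day 90. Mortality is analysed separately in SAP 7.5.2.2, as a Kaplan-Meier event rate at 90 days.

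**The concern.** The endpoint is meant to describe functional status at about 90 days, with death as the worst category. The death rule depends on the score being missing, and a subject rated early in the window has a score. Such a subject can appear as functionally independent at 90 days in one table and as dead by 90 days in another.

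Separately, a score taken months after day 90 enters the main rate under a 90-day label. SAP 7.14 expects late assessments, so this is not a remote case. No planned analysis uses the protocol's own ±14 days; the only closed-window analysis uses ±15.

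At stake is whether the reported rate means what its label says and agrees with the mortality result beside it.

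**Working it through.** **The plan's own figure.** The only computed precision figure in the documents is for the primary endpoint: 1.96 × √(0.8 × 0.2 / 95) = 0.0804, which matches the stated 8.0%. It concerns mTICI; no figure is given for mRS. I borrow only n = 100 × (1 − 0.05) = 95 as an assumed number of evaluable subjects.

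**Windows** (procedure = day 0, SAP 7.1)
- Protocol: 90 ± 14 = days 76 to 104.
- SAP 3: 90 ± 15 = days 75 to 105.
- Main mRS analysis: day 75 onward, no upper limit.

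**Defect 1: the death rule.** Take a subject rated mRS 2 on day 76 who dies on day 86.

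| Rule | Applied to this subject |
|---|---|
| Main mRS window (SAP 7.5.2.1) | Day 76 qualifies; the score is not missing |
| mRS 6 for death (SAP 7.5.2.1) | Not triggered, because no score is missing |
| mRS 0-2 at 90 days | Success |
| 90-day mortality (SAP 7.5.2.2) | Death on day 86, an event |

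Day 76 also lies inside the ±15 and ±14 windows, so the ±15-day sensitivity analysis gives the same answer. The cause is the dependence on a missing score, not the open upper end.

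Size: 1/95 = 1.05 points per subject; three such subjects would be 3/95 = 3.2 points. Correcting the rule removes the subject from the numerator and leaves the denominator unchanged, so the present rule can only inflate the rate. A subject rated 3-5 who then dies does not change the 0-2 rate, but would change the category and shift tables in SAP 7.13.

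**Defect 2: the open upper end.** The documents give no mRS rate and no count of late visits. Assumptions: 95 evaluable subjects, of whom L are assessed after day 105; rate p of mRS 0-2 among those in the ±15-day window (40-60%); rate q among the late ones.

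Main rate − ±15-day rate = [(95 − L)p + Lq]/95 − p = L(q − p)/95

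With q − p = ±20 points:
- L = 5: 5 × 20/95 = 1.1 points
- L = 10: 10 × 20/95 = 2.1 points
- L = 20: 20 × 20/95 = 4.2 points

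Each applies in either direction and does not depend on p. If q = p, the shift is 0.

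Exact 95% intervals at n = 95, for scale:

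| Successes | Rate | 95% interval | Half-width |
|---|---|---|---|
| 38 | 40.0% | 30.1-50.6% | 10.3 points |
| 48 | 50.5% | 40.1-60.9% | 10.4 points |
| 57 | 60.0% | 49.4-69.9% | 10.3 points |

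**The case against.** The strongest reply is that the timing issue is already largely handled. The change is declared with a reason, a closed-window analysis is prespecified, and out-of-window scores are listed. The endpoint is secondary and descriptive, and SAP 4 says the intervals are not for inference. All of that stands and limits the weight of the second defect. What remains is that the open-window figure is the headline, the protocol window is reported nowhere, and the listing does not say which 90-day window it means.

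On the death rule, it can be said that the case is rare: it needs a rating of 0-2 followed by death within about two weeks. That is fair, and the documents give no frequency. But the rule gives a contradictory result whenever the case occurs, and none of the planned sensitivity analyses repairs it.

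Three stronger readings are tempting and are not supported:
- *The missing upper limit admits non-independent ratings.* Unscheduled mRS is collected only up to the 90-day visit (Protocol 7.7 and Table 1), so it cannot enter through the late end. The protocol requires an independent rater, and SAP 3 says "Data will be summarized by scheduled visit". SAP 7.11 names unscheduled scores as a source for carrying forward, which suggests they are not main-analysis data. The words of SAP 7.14 leave room for doubt about an unscheduled rating from day 75, but that is an ambiguity and not a stated rule.
- *The SAP picks the latest of several scores.* The provision that "the most recent measurement with non-missing values will be used unless specified otherwise" covers only repeats at the same visit. It does not choose between visits.
- *Late scores bias the rate upward.* Nothing in the documents gives recovery after day 90. The open window could also lower the rate: the mRS 6 rule has no day limit, so an unassessed subject who dies after day 105 could be scored 6.

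**Conclusion.** Both defects hold, as separate points.

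The death rule is the firmer one. As written it lets a subject dead by day 90 count as a 90-day good outcome. The effect is 1.05 points per subject at an assumed n = 95, always upward. How many such subjects there will be is unknown and may be none. The gap exists under the ±14, ±15 and open windows alike, so closing the window would not remove it.

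The open upper end is a labelling and reporting weakness. Its direction is unknown. Under the assumptions above (5 to 20 late subjects, a 20-point difference) its size is about 1 to 4 points either way, which is small against a half-width of about 10 points. A reader might infer that the headline rate is inflated by late recovery; the documents do not show that.

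**What to change.** 1. In SAP 7.5.2.1, score mRS 6 for any death on or before day 90, even where an earlier in-window mRS exists.
2. Report the rate for the protocol window (±14 days) in the same table as the open-window rate, with the distribution of assessment days. Reconcile the SAP's ±15 days with the protocol's ±14.
3. State that the qualifying score is the 90-day-visit rating by the independent evaluator. This clarifies ambiguous wording.
4. Use the same set of scores, and the same death rule, for the 90-day category and shift tables in SAP 7.13.

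I do not propose a fixed upper cut-off day for the main analysis. The documents offer no basis for choosing one, and because subjects with scores missing for reasons other than death are excluded, a cut-off would exchange timing error for selection by follow-up. Showing both rates avoids that choice.

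The cost is SAP wording, one extra table row, and a rate that may be slightly less favourable. No new data are needed: assessment and death dates are already required by the planned analyses.

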7.5.2.2 Secondary Safety Endpoints

Device-related SAEs and all-cause mortality, Kaplan-Meier analysis (using product limit estimates) will be applied. Kaplan-Meier event rate and its associated two-sided 95% CIs using log-log transformation will be reported, the estimate of standard error will be computed using Greenwood's formula.

- **Devices related serious adverse events (SAEs) within 90 days of follow up as determined by an independent Clinical Events Committee**

Kaplan-Meier analysis will be performed to analyze the device related SAE rate within 90 days. Device related SAEs are considered as events; where the event date is the date of first event. Subjects without events will be censored at the date of last contact. The event rate at 90 days with associated 95% CIs will be provided. Device related SAEs beyond 90 days will be listed.

- **sICH at 24h post procedure specified according to the Heidelberg Bleeding Classification (HBC) as determined by an independent Clinical Events Committee**

sICH at 24 hours post procedure as specified by HBC will be assessed. The number and percentage of subjects with events will be summarized with CIs.

- **NIHSS at 24h post procedure**

The observed NIHSS total score at 24 hours post-procedure and changes from the baseline score will be summarized.

- **90 Day All-Cause Mortality**

Kaplan-Meier analysis will be performed to analyze all-cause mortality within 90 days. All-cause mortality is considered as the event; where the event date is the date of mortality. Subjects without events will be censored at the date of last contact. The event rate at 90 days with associated 95% CIs will be provided. Deaths beyond the 90 days will be listed.

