### 8.1.2. Serious Adverse Event (SAE)

A serious adverse event (SAE) is defined (ISO 14155:2020) as an adverse event that led to any of the following:

- Death
- Serious deterioration in the health of the subject, users, or other persons as defined by one or more of the following:
  - a life-threatening illness or injury, or
  - a permanent impairment of a body structure or a body function including chronic diseases, or
  - in-patient or prolonged hospitalization, or
  - medical or surgical intervention to prevent life-threatening illness or injury or permanent impairment to a body structure or a body function
- Fetal distress, fetal death or a congenital abnormality or birth defect including physical or mental impairment

Note: Planned hospitalization for a pre-existing condition, or a procedure required by the clinical investigation plan, without serious deterioration in health, is not considered a serious adverse event.

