#### 10.5.4.2.2. Secondary Safety Endpoints

- **Devices related serious adverse events within 90 days of follow up**  
The number and percentage of subjects with device related SAEs will be summarized. The number of events will also be summarized. Device relatedness will be adjudicated by an independent CEC.
- **sICH at 24h post procedure specified according to the Heidelberg Bleeding Classification (HBC)**  
sICH at 24 hours post procedure as specified by HBC will be assessed by an independent CEC. The number and percentage as well as the two-sided 95% confidence intervals around the percentage will be summarized.
- **NIHSS at 24h post procedure**  
The observed NIHSS total score at 24 hours post-procedure and changes from the baseline score will be summarized.
- **90 Day All-Cause Mortality**  
All-cause mortality at 90 days post-procedure will be summarized. Two-sided exact 95% confidence intervals will be constructed around the percentage.

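### Kaplan-Meier for device-related SAEs in effect censors unrelated deaths, so it can overstate the share of treated subjects affected; a cumulative incidence estimate avoids this.

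*SAP*

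**What the plan says.** Protocol 10.5.4.2.2 plans a simple summary for this endpoint: "The number and percentage of subjects with device related SAEs will be summarized. The number of events will also be summarized". It names no confidence interval here. For mortality, the same section does: "All-cause mortality at 90 days post-procedure will be summarized. Two-sided exact 95% confidence intervals will be constructed around the percentage".

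SAP 7.5.2.2 uses a time-to-event estimate for both endpoints. For device-related SAEs it says "Kaplan-Meier analysis will be performed to analyze the device related SAE rate within 90 days". The event is the first occurrence ("Device related SAEs are considered as events; where the event date is the date of first event"), and the censoring rule is "Subjects without events will be censored at the date of last contact". On reporting: "Kaplan-Meier event rate and its associated two-sided 95% CIs using log-log transformation will be reported". The section does not say how a death without a device-related SAE is handled, and no competing-event rule appears elsewhere in the SAP.

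Protocol 8.1.2 introduces the SAE definition with "A serious adverse event (SAE) is defined (ISO 14155:2020) as an adverse event that led to any of the following", and death heads the list that follows. A device-related death is therefore an event, not a censoring.

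SAP 7.14, which lists changes from planned analyses, records only the wider mRS window. It mentions 90-day mortality and SAEs by name but not the move from percentages to Kaplan-Meier.

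**The concern.** Kaplan-Meier censoring assumes that a censored subject could still have the event later, at the same rate as those still followed. That is reasonable for a subject who withdraws. It is not reasonable for one who has died, who can have no further device-related SAE. With such deaths censored, one minus Kaplan-Meier estimates risk in a hypothetical setting without those deaths. It can equal or exceed the cumulative incidence but never fall below it.

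The study is descriptive, with no hypothesis tests, so the estimates themselves are the product. Protocol 1.3 reports no earlier clinical investigation of the device, and SAP 7.9 sends interim summaries into regulatory submissions. The device safety figure should answer the protocol's question: what share of treated subjects had a device-related SAE within 90 days?

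**Working it through.** **The plan's own figure.** The only calculated figure in the documents is the margin of error for the primary endpoint: 1.96 × √(0.8 × 0.2 / 95) = 8.04%, which matches the stated 8.0%. No rate is given for device-related SAEs or for mortality, so every rate below is an assumption.

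**Inputs from the documents.** About 100 subjects; first device-related SAE as the event; censoring at last contact; evaluation at 90 days.

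**Formulas.** Take n subjects, d0 events on day 0, then m deaths without a device-related SAE, then d1 later events, with no withdrawals:

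- 1 − KM = 1 − [(n − d0)/n] × [(n − d0 − m − d1)/(n − d0 − m)]
- Cumulative incidence (Aalen-Johansen) = d0/n + [(n − d0 − m)/n] × [d1/(n − d0 − m)] = (d0 + d1)/n

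Without withdrawals, Aalen-Johansen therefore equals the simple percentage.

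**Four events, 15 early unrelated deaths, n = 100** (cumulative incidence 4.0%):

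- All 4 on day 0: 1 − 96/100 = 4.00%
- 2 on day 0, 2 on day 45: 1 − 0.98 × 81/83 = 4.36%
- All 4 on day 60: 1 − 81/85 = 4.71%

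**Five events, 20 unrelated deaths spread over days 1 to 30, n = 100** (cumulative incidence 5.0%):

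- All 5 on day 0: 5.00%
- 4 on day 0, 1 on day 60: 1 − 0.96 × 75/76 = 5.26%
- On days 5, 20, 40, 60 and 80: 1 − (96/97) × (85/86) × (77/78) × (76/77) × (75/76) = 5.94%
- All between days 60 and 80: 1 − 75/80 = 6.25%

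**Wider range.** This model places a chosen share of device-related SAEs on day 0 and gives the rest a constant hazard. Deaths without a device-related SAE run from 5% to 30%, either at a constant hazard or with half in the first 7 days.

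| True 90-day incidence | 1 − KM, lowest | 1 − KM, highest |
|---|---|---|
| 2% | 2.00% | 2.55% |
| 5% | 5.00% | 6.39% |
| 10% | 10.00% | 12.81% |

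The lowest value has all events on day 0. The highest has none on day 0, 30% deaths and half of those within 7 days. At a true 5% with 20% deaths, Kaplan-Meier gives 5.6% to 5.8% with no events on day 0, and 5.1% to 5.2% with 80% of them there.

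**Sampling error for scale.** The exact 95% CI for 5/100 is 1.6% to 11.3%.

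**Not every gap is competing-risk bias.** With no deaths, 4 events on day 0, one on day 88 and last contacts spread over days 76 to 104, 55 subjects are at risk on day 88. Kaplan-Meier gives 1 − 0.96 × 54/55 = 5.75% against a simple 5.00%. That gap comes from incomplete follow-up, which the simple percentage ignores.

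**The case against.** The best defence is that the effect is conditional and probably small. The catheter is used during the thrombectomy and is not described as left in place, so device-related SAEs may well cluster on the procedure day, where the bias vanishes. The safety endpoint treats an event as device-related when the device cannot be excluded as a cause, so only deaths judged unrelated are censored. Any error overstates device risk and cannot hide harm. Kaplan-Meier also handles withdrawals, which plain n/N does not. The general convention in SAP 7.1 might be read as keeping a number and percentage beside the Kaplan-Meier rate.

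Most of this stands, and it limits the size of the point. It does not remove it. The documents give no event timing, SAP 7.5.2.2 leaves the handling of death unstated, and SAP 7.1 does not clearly restore the protocol's summary for this endpoint. Aalen-Johansen keeps the advantage over withdrawals without the competing-death bias.

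A reader might infer more than the documents support:

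- That the Kaplan-Meier figure will contradict the adverse event table in SAP 7.8. That table has rows for SAEs and for device-related AEs but none for device-related SAEs, so it offers no direct comparison.
- That the protocol requires an exact interval here. It specifies one for mortality, not for this endpoint.
- That death must be frequent because it is an endpoint. Endpoint status says nothing about frequency.
- That Kaplan-Meier is also biased for mortality. There death is the event, so no competing risk arises; that change is only an unlisted departure from the protocol's percentage with exact interval.

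**Conclusion.** The concern holds in a conditional form. As written, SAP 7.5.2.2 can overstate the 90-day share of treated subjects with a device-related SAE, and does so when such an event follows an unrelated death. Over the assumed range the excess is 0 to about 0.6 points at a true 2%, 0 to 1.4 points at 5% and 0 to 2.8 points at 10%, with the upper values needing heavy early mortality and no procedure-day events. That is modest beside the sampling error with 100 subjects.

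This rests on two readings. Last contact for a subject who dies is taken as the death, which follows from the censoring rule but is not stated. Only deaths that are not device-related SAEs are affected. The unlisted departure from the protocol's summary needs no assumption about rates: it is visible by comparing Protocol 10.5.4.2.2 with SAP 7.5.2.2 and 7.14.

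**What to change.** In SAP 7.5.2.2, replace Kaplan-Meier for device-related SAEs with the Aalen-Johansen cumulative incidence at 90 days. Name death without a device-related SAE as the competing event, and censor withdrawal and loss to follow-up at last contact.

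Beside it, report the protocol's number and percentage of subjects and number of events. An exact 95% CI may be added, consistent with SAP 7.5.2, and should be described as an addition to the protocol.

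Keep Kaplan-Meier for all-cause mortality if wanted. Record both departures from the protocol's percentages in SAP 7.14. While editing, reconcile SAP 7.14, which ties 90-day SAEs to a window of ±15 days, with SAP 7.5.2.2, which gives the rate at 90 days and only lists later events.

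The cost is SAP wording and slightly more programming, with no new data. Plain n/N alone would be simpler, but it counts subjects lost before 90 days as event-free, and the sample size section allows for up to 5% attrition.
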